# 7.5 PATIENTS DISPOSITION

Disposition of patients will be presented by treatment group for the randomized population.

The number of patients included in each of the randomized, safety, ITT, PP will be summarised for each treatment group and for placebo subjects by cohort and overall.

1.0/30/10/2018 Page 17 of 28

Randomized patients who discontinued from the study prematurely will also be presented with a breakdown of the reasons for discontinuation by treatment group for the randomized population.

Major and minor protocol violations will also be summarised for each treatment group in the randomized population.

# 7.6 DEMOGRAPHIC AND SCREENING/BASELINE CHARACTERISTICS

The baseline demographic characteristics will be summarised by treatment group, and for placebo subjects by cohort and overall, by means of descriptive statistics.

The following characteristics will be provided for ITT population:

- Age (years)
- Gender (male/female)
- Race
- Smoking habits
- Alcohol consumption Alcohol Breath test
- Viral serology
- Digoxin assay

# Past disease and concomitant disease

Past disease and concomitant diseases will be coded using Medical Dictionary for regulatory activities (MedDRA) dictionary (version 16.0) and frequency distributions and percentages will be summarised by treatment group for the ITT population by System Organ Class (SOC) and PT.

### Medications

Medications will be coded using World Health Organization Drug Dictionary (WHO DD), 2012Q1 (1st Quarter of 2012).

Previous medications, medications maintained during the treatment period and concomitant medications will be summarised by treatment group for the ITT population through frequency distributions and Anatomical Main Group (1st level of the Anatomical Therapeutic Chemical (ATC) classification), Chemical Subgroup (4th level of the ATC classification) and Preferred Name.

Subjects experiencing more than one medication classified in the same category (previous medications, medications maintained during the treatment period, concomitant medications) within the same anatomical main group, chemical subgroup and preferred name will be counted only once.

# Echocardiographic parameters at baseline

Descriptive statistics will be presented for the following echocardiographic parameters at baseline: EDD, ESD, LV end diastolic volume, LV end systolic volume, LVEF, 2D global longitudinal strain, Left atrium diameter, Left atrium area, Left atrium volume, ERO, CI, SVI, E, A, E/A ratio, Sa, Ea, E/Ea ratio, PAPs,

1.0/30/10/2018 Page 18 of 28

TAPSE, Right ventricle Sa, Inferior vena cava diameter and Mitral regurgitation (None/Mild/Moderate/Severe).

No formal comparison between treatment groups on baseline characteristics will be done.

#### 7.7 ANALYSIS OF EFFICACY

# 7.7.1 Primary efficacy endpoint

Analysis will be performed separately for each cohort on ITT and PP populations.

E/Ea ratio will be summarized at each timepoint by treatment group by means of descriptive statistics.

Comparisons between treatment groups will be done using an ANOVA with change from baseline in E/Ea at 24 hours as dependent variable, and treatment as covariate.

The number of patients and the number of patients considered in the model will be provided by treatment. P-values of the fixed effects and covariates will also be presented.

The adjusted means for treatments and 95% CIs will be presented. The difference between the adjusted means for Istaroxime groups versus Placebo will be calculated with the 95% CIs and p-values.

The primary comparison will be Istaroxime 0.5  $\mu$ g/kg/min versus Placebo at 24 hours based on Cohort 1 subjects only. Highest dose of Istaroxime (1.0  $\mu$ g/kg/min) versus Placebo will be tested as a secondary comparison based on Cohort 2 subjects only.

The same analysis will be repeated for change from baseline in E/Ea at 6 hours. All treatment comparisons at 6 hours will be secondary analyses.

E/Ea ratio will also be summarized separated by cohort at each timepoint by treatment group by means of descriptive statistics.

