5.2 Drug Blind Code

The computer generated randomization list stratified by centre and atrial fibrillation (Yes/No) will be prepared via a computerised method. Starting from the lowest number provided, in each center and and atrial fibrillation, at Day 1, patients will be sequentially assigned to the next randomization number, following the order in which they present themselves for the study. The investigator will keep the code break envelopes in a locked, secure storage facility.

A code break envelope can only be opened in an emergency situation (mainly SUSAR occurrence) where the investigator considers it essential to know which treatment the subject was taking. If possible, it is recommended that the investigator contacts the Sponsor before opening an envelope. The monitor shall be promptly notified when a treatment code envelope is opened. The investigator shall provide a certified explanation of why the treatment code was opened in the Case Report Form for the subject or directly on the opened treatment code envelope.

IMPORTANT: The randomization codes will only be disclosed to the laboratory in charge of the bioanalytical assay (plasma and urine PK assessment) of istaroxime and its metabolites, in order to prevent analyses of samples from patients who have received placebo. This laboratory will re-code identifiers of patients, allowing only to differentiate but not to identify the patients, in order to maintain blinding integrity for the other assessments of the study, until database lock. PK results will be maintained separate from the electronic CRF data until database lock at study completion.

Emergency Un-blinding: 1) Un-blinding condition: any emergencies of unknown origin that occur to the subject during the trial, should find out the medication type, or the subject asks to quit and wants to know the medication type; 2) Un-blinding register: the principle investigator opens and reads the emergency letter of corresponding number, recording the reading date and reason in detail, and signs his/her name; 3) Un-blinding disposal: once the emergency letter is **Protocol N°: CVT-CV-002**

read, the corresponding case is regarded as drop-out.

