5.4 Emergency Envelope/Emergency Unblinding Card

Emergency envelope is prepared for SAE happening, one opens the envelope to rescue in time, and avoid overall un-blinding. "A randomized, double-blind clinical study of Istaroxime", and the randomization number are printed on the envelopes. The emergency envelope draft is as follow:

Double-	blind clinical study emergency	
Un-blinding record Drug Randomization No.: Study project: A randomized, double-blind clinical study of Istaroxime		
_	Therapeutics Company Limited	
	esponsible Sites: XX	
The subject of the	nis Randomization No. is randomly divided into:	
	Test group: Istaroxime 0.5 mcg/kg	
	Test group: Istaroxime 1.0 mcg/kg	
	Control group: Placebo	
Reason for emergency unblinding:		
Study center:		
Signature of investigator: Date:		
Signature of principal investigator: Date: Note: the case should withdraw from the study after emergency un-blinding		

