5.7 Concomitant Medication

All oral treatments, are permitted during the study with the exception of positive inotropic agents.

Dosage of oral HF medications must remain stable for at least 6 hours before study entry, during the entire treatment period (24-hour infusion), until 72 hours (on Day 4) after the start

of infusion on Day 1. Concomitant medications should be administered in the prerandomization phase and after at least 6 hours from the initiation of study drug infusion, if possible.

Intravenous diuretics administered during the screening period to stabilize the patient's condition will be permitted during the treatment period at stable doses, unless changes are required due to clinically relevant variations of the patient's condition.

Any introduction of new drugs or increase of the dosage of oral or i.v. medications for the treatment of heart failure, during treatment and till the 72 hours after the start of infusion (on day 4), will be considered as "rescue medication".

Patient supplementation of magnesium or potassium, prior to randomization, will not be considered as a change of the standardized therapy but just as a supplementation to maintain serum electrolytes within the normal ranges.

Administration of prior medications (i.e. drug treatments administered during the last month) and concomitant medications/therapies (i.e. medications ongoing at admission time and with a start date between admission to the research center and Day 4 or discharge) must be reported on the appropriate medication pages of the CRF, including dosage information, dates and time of administration and reasons for use. The international non-proprietary name and the trade name in brackets should be used for concomitant medications. The total daily dose or the stat dose, if appropriate, should also be reported. Rescue therapies will be recorded on the specific rescue medication page, recording the same information as for concomitant therapies, plus the time of administration of each single dose.

In case an inotrope should be necessary as rescue medication during the investigational product infusion period, the investigational product infusion should be terminated.

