- 6) NT pro-BNP at baseline and at the end of 24 hours infusion
- 7) Blood sample collection for metabolites and PK (at pre-dose, 0.5, 3, 6, 12, 24 hours after start of infusion and 0.25, 0.5, 1, 4, 12, 24, 48 hours after the end of infusion) in a subset of Italian patients and in a subset of Chinese patients pharmacokinetics and metabolism of istaroxime shall also be studied;
- 8) Vital signs (including arterial oxygen saturation and dyspnoea at pre-dose, 3, 6, 12 and 24 hours after the start of infusion);
- 9) 12-lead ECG profile (pre-dose, 3, 6, 12 hours and between 23 hours and 23 hours 55 minutes after infusion, totally 5 times, each time 3 measurements);
- 10)Stop 24-hour Holter ECG (Day -1 recording; Holter ECG monitor stops automatically 24 hours after the recording has been started;
- 11) Start 24-hour Holter ECG (Day 1 recording; to be started immediately before initiation of the study drug infusion);
- 12) Echocardiography at baseline and 6 and 24 hours after infusion start;
- 13) 24-hours urine collections for measurement of istaroxime and its metabolites and urinary

- creatinine for the calculation of the creatinine clearance
- 14) Blood collection for K+ and eGFR between 23 hours and 30 minutes and 23 hours and 55 minutes since infusion start
- 15) Concomitant medication monitoring (including chronic medication; dose, date and time must be recorded in the CRF);
- 16) Adverse events monitoring.

♦ Post-treatment period (Day 2 to Day 4)

Evaluations on Day 2 (end of the 24 hour infusion) include:

- 1) Vital signs (including arterial oxygen saturation and dyspnoea);
- 2) 12-lead ECG (triple ECGs) (between 23 hours and 23 hours 55 minutes since infusion start);
- 3) Stop 24-hour Holter ECG (Day 1 recording; to be stopped immediately after the end of study drug infusion;
- 4) Start 24-hour Holter ECG (Day 2 recording);
- 5) Stop istaroxime or placebo infusion (date and time of infusion end must be recorded in the CRF);
- 6) Serum potassium levels and 24-hour urine collection for measurement of istaroxime metabolites and urinary creatinine for calculation of the creatinine clearance;
- 7) Serum creatine clearance and calculation of eGFR;

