15. QUALITY CONTROL AND QUALITY ASSURANCE

During the trial, monitor will be appointed by Sponsor to visit the study centers regularly, in order to ensure rigorous performance of all contents in the protocol and accuracy of study materials.

Investigators must attend unified training to unify the record manner and the judgment standard.

- the clinical trial process should be strictly conducted in a blind state.
- Investigators should fill in the CRF accurately, detailed, and seriously according to the requirements, to insure that contents of the CRF are true and credible;
- Judgment standard of laboratory examination abnormality should be subject to the normal range of the centers;
- •All observation results and findings of the trial should be verified to ensure the reliability of the data and that each conclusion comes from source data. Corresponding data management should be taken during the trial and data processing period;
- For possible drop-out, active measures should be taken to keep the dropout rate within 20%.

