# 1.1 CHANGES FROM PROTOCOL

The analysis of echocardiographic parameters is changed from the protocol:

- The analysis of echocardiographic parameters will be performed separately for each cohort, instead of performed on the combined cohorts.
- An analysis of variance (ANOVA) model with treatment as covariate is now the primary analysis, instead of a mixed model for repeated measures (MMRM) including treatment and additional covariates.
- Missing response data will not be imputed in the ANOVA analysis.

The justification for these changes are documented in the Memo to File prepared by [name], dated 24Oct2018, entitled: Change in analysis of echocardiographic parameters.

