# 7.0 STATISTICAL METHODOLOGY

## 7.1 HANDLING OF MISSING DATA

The number of patients with missing data will be presented under the "Missing" category, if present. Missing values will be included in the denominator count when computing percentages.

When continuous data are being summarised, only the non-missing values will be evaluated for computing summary statistics.

Missing or incomplete data will be treated as described in sections 6.1, 6.3 and 6.4.

There will be no imputation of missing echocardiographic data.

Other critical missing data will be discussed prior to treatment unblinding, if any. Decisions will be taken during the blind review of the data and will be fully documented in the Data Review Report.

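### The primary 24 h E/Ea ANOVA leaves out patients who have a 6 h echo but no 24 h echo; a covariate-free mixed model on both echoes would keep them and gives the same answer when none is missing

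*SAP*

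**What the plan says.** The protocol schedules "Echocardiography at baseline and 6 and 24 hours after infusion start" (section 7), and a further echo at 48 h that section 8 treats as exploratory. Protocol 14.2 planned a repeated-measures mixed model with covariates for E/Ea.

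The SAP replaces that model. Section 7.7.1 states: "Comparisons between treatment groups will be done using an ANOVA with change from baseline in E/Ea at 24 hours as dependent variable". Treatment is the only term (7.2, and the PROC GLM code in 9.0), and the cohorts are analysed separately, 40 istaroxime against 20 placebo. On missing data, SAP 1.1 says "Missing response data will not be imputed in the ANOVA analysis" and SAP 7.1 says "There will be no imputation of missing echocardiographic data". The 6 h change gets its own secondary ANOVA.

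The ITT population (SAP 5.1) is the primary efficacy population and requires only one efficacy evaluation after baseline. SAP 1.1 declares the change of method and refers to a memo for the reasons. That memo is not among the documents, so this point is about the method and does not allege an inconsistency.

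**The concern.** A patient with the 6 h echo but not the 24 h echo is in the ITT population but not in the primary model. The 24 h difference is then unbiased only if, within each arm, losing the 24 h echo is unrelated to E/Ea. In acutely decompensated patients the ones doing badly at 6 h could be the ones without a 24 h scan, and their arm would then look better than it was. If the same rule acts in both arms, a real effect is diluted and power falls. If it acts mainly on istaroxime, the bias favours the drug.

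Nothing else in the SAP repairs this:

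- The per-protocol analysis is a subset of ITT.
- The MANOVA is run separately at 6 h and 24 h.
- The mixed model now serves only the dyspnoea score.
- SAP 7.9 lists no other analysis.
- Counts of patients in the model show the loss but do not adjust for it.

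**Working it through.** **Inputs from the documents.** 40 v 20 per cohort, two-sided 5% level (SAP 4.0, 7.4). Protocol 1.2 reports earlier E/Ea changes at 6 h of -3.8 (p=0.03) and -1.12 (p=0.059). SAP 4.1 gives 29 patients per group for the first of these. There is no planned power figure to reproduce, because both documents state that no formal sample size calculation was made.

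**Assumptions.** 29 per group is used for both doses, and the reported changes are read as differences from placebo. The missing rate is 5 to 20%. The 6 h to 24 h correlation r is 0.5 to 0.8 in the main runs. The log-odds of losing the 24 h echo rise by 1 or 2 per SD worse at 6 h (odds ratio 2.7 or 7.4). The documents give none of these last three.

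**Step 1, scale.** SE = difference / t(56) and SD = SE / sqrt(2/29).

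- 0.5 dose: 3.8/2.227 = 1.706; SD = 6.50; effect 0.58 SD.
- 1.0 dose: 1.12/1.927 = 0.581; SD = 2.21; effect 0.51 SD.

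The two implied SDs disagree, so the main results are in SD units.

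**Step 2, equality on complete data.** One simulated set of 60 gave the ANOVA a difference of -1.9623, SE 1.46781, 58 df. The mixed model gave -1.9623, SE 1.46781. After nine 24 h values were deleted, the ANOVA used 51 patients (SE 1.617) and the mixed model all 60 (SE 1.567).

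**Step 3, why the two differ when data are missing.** For each arm the mixed model estimates

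24 h mean = completers' 24 h mean + b × (6 h mean of all - 6 h mean of completers),

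where b is the pooled within-arm slope of the 24 h change on the 6 h change. The ANOVA omits the second term.

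A hand check: let placebo patients above the placebo mean at 6 h (the worse half) lose the 24 h echo with probability 40%, which is 20% of placebo overall, and let no istaroxime patient lose it. Each half of a normal distribution has its mean 0.798 SD from the centre. The completers' 6 h mean is (-0.5 × 0.798 + 0.3 × 0.798)/0.8 = -0.20 SD, or -1.30 units at SD 6.5. Multiplying by r = 0.3, 0.5, 0.7 makes placebo look better by 0.39, 0.65, 0.91. A true -3.8 becomes about -3.41, -3.15, -2.89. Simulation gave -3.42, -3.17, -2.90 for the ANOVA and about -3.8 each time for the mixed model.

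**Step 4, simulated size** (20,000 trials per cell; ranges are over r and the odds ratio).

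Same rule in both arms, true effect 0.58 SD, full-data power 55%:

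| Placebo missing | ANOVA power | Mixed model power |
|---|---|---|
| 20% | 39-44% | 47-51% |
| 10% | 46-50% | 51-53% |
| 5% | 50-52% | 52-54% |

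In the first row istaroxime loses 10-13%, because treated patients do better at 6 h. Repeat runs put the gain at 5% missing at about 1 to 5 points.

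No drug effect, false-positive rate:

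| Missing, istaroxime v placebo | ANOVA | Mixed model |
|---|---|---|
| 20% v 0% | 5.9-11.9% | 4.6-5.0% |
| 10% v 0% | 5.4-7.3% | 4.6-5.0% |
| 5% v 0% | 5.1-5.9% | 4.6-4.9% |
| 20% v 10% | 5.2-6.6% | not tabulated |
| 10% v 5% | 5.1-5.6% | not tabulated |

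Repeats of the first row reached about 13% for the ANOVA. Its ANOVA bias is 0.09 to 0.21 SD. With no drug effect and equal loss in both arms, both methods stay near 5%.

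If 20% are lost completely at random, both methods are unbiased. The mixed model then cuts the variance by 1-2% (r = 0.3), 4-5% (0.5) or about 10% (0.7).

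**The case against.** The strongest reply is that nothing in the documents shows a 24 h echo being missed often.

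- The rescue rule reads: "In case an inotrope should be necessary as rescue medication during the investigational product infusion period, the investigational product infusion should be terminated". It stops the infusion; it neither withdraws the patient nor cancels the scan.
- After emergency unblinding, "the corresponding case is regarded as drop-out" and "the case should withdraw from the study after emergency un-blinding" (Protocol 5.2 and 5.4). That could remove a scan, but it should be rare and can happen at any time to Day 30, mostly after the 24 h echo.
- The protocol's "active measures should be taken to keep the dropout rate within 20" per cent is a goal for the whole 31-day study. At 24 h the patient is still in hospital: the SAP's formula for length of stay counts at least four days for everyone.

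All of this stands. A reader might infer that one echo in five will be missing, or that the primary test has a false-positive rate near 12%. The documents support neither. That rate needs one-sided loss at the whole-study limit, and its top value also needs the steepest odds and the highest correlation.

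Other replies carry part of the way. With the same rule in both arms the bias works against istaroxime, and much of the lost power is simply lost sample size: random loss of 20% on placebo and 11% on istaroxime gives 47% ANOVA power against 55%. The 48 h echo could also carry information, and the recommended model does not use it. The unseen memo may have considered missing data. Missing at random is itself an assumption: if loss depends on the 24 h value (20%, istaroxime only, no effect), mixed-model bias is still 0.06-0.21 SD with 5.9-12.2% false positives, against 0.17-0.26 SD and 10.0-16.9% for the ANOVA. None of this gives a reason to discard the 6 h value.

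**Conclusion.** The point holds as a low-cost improvement to the primary analysis. It is not evidence that the planned test is seriously invalid. The plan drops ITT patients who have only the 6 h echo from the primary comparison, and no planned analysis recovers them.

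The consequence is small if few 24 h echoes are missing. It is material only if loss is substantial, depends on the 6 h result and, for false positives, falls almost wholly on istaroxime. These sizes rest on assumed missing rates, correlations and odds. The equality with the ANOVA on complete data does not rest on them. It does require the treatment-by-timepoint interaction, an unstructured covariance and no other covariates.

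**What to change.** In SAP 7.7.1, for each cohort, estimate the 24 h treatment difference from a mixed model on the 6 h and 24 h E/Ea changes. Use treatment, timepoint and treatment-by-timepoint, an unstructured covariance, Kenward-Roger degrees of freedom and no other covariates. Keep the 24 h ANOVA as a supportive analysis.

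Three further edits are needed:

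- Amend SAP 1.1 and 7.2, which now describe the echo analysis as an ANOVA.
- In the SAP 9.0 mixed-model code, delete the covariates and add a request for the 24 h treatment difference (a DIFF option on LSMEANS, or an ESTIMATE statement). The present code prints means only.
- State whether the secondary echo parameters in SAP 7.7.2 follow the same model, since that section ties them to the primary method.

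The cost is modest wording and programming work, with no change to patient care. The analysis then relies on data missing at random given the 6 h value, which is weaker than the ANOVA's requirement that loss be unrelated to E/Ea. Patients with neither a 6 h nor a 24 h echo are still not recovered.

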### 7.2 COVARIATES AND SUBGROUPS

Linear Mixed Models for Repeated Measures (MMRM) will include treatment, centre, timepoint, gender, baseline cTnT (normal <URL, abnormal ≥URL), atrial fibrillation (Yes/No) and treatment\*timepoint interaction as fixed effects and baseline and baseline\*timepoint interaction as covariates.

Analysis of Covariance (ANCOVA) models will include treatment, centre, gender, baseline cTnT (normal <URL, abnormal ≥URL) and atrial fibrillation (Yes/No) as fixed effects and baseline as covariate.

ANOVA models for echocardiographic parameters will include treatment only. For analysis of Cohort 1, treatment is defined as (0.5 µg/kg/min dose, placebo). For analysis of Cohort 2, treatment is defined as (1.0 µg/kg/min dose, placebo).

All baseline values considered in the statistical analyses have been defined in the paragraph 6.6.

1.0/30/10/2018 Page 16 of 28

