# 7.4 GENERAL METHODOLOGY

Descriptive statistics will be provided for all variables in the summary tables by treatment group according to the type of variable summarized.

Quantitative variables will be summarised by using n, mean, standard deviation (SD), 95% confidence interval (CI) of the mean, median and range (minimum and maximum). Categorical variables will be summarised by using frequency distributions and percentages.

Hypothesis testing will be carried out at the alpha = 0.05 level (two-sided) when comparing treatments. For all inferential analyses, p-value will be rounded to three decimal places. Statistical significance will be declared if the rounded p-value will be less than or equal to 0.05.

Statistical analyses will be carried-out pooling together the patients treated with placebo in the two groups with the exception of the echocardiographic parameters that will be analysed separately for each cohort.

All data collected in the CRF will be presented in the listings.

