# Echocardiographic parameters

The following secondary endpoints:

o LVEF

1.0/30/10/2018 Page 19 of 28

- o LV end systolic and end diastolic volumes
- o SVI, and CI
- o E, A, E/A ratio
- Sa (tissue doppler parameters)
- o Ea and TAPSE

will be summarized at each timepoint by treatment group by means of descriptive statistics.

Comparison between treatment groups will be done using the ANOVA similar to the one used for the primary efficacy endpoint. Only change from baseline echocardiographic data at 6 hours and 24 hours values will be analyzed.

The global test using multivariate analysis of variance (MANOVA) considering multiple echocardiographic parameters will also be performed separately at 6 and 24 hours and by cohort for echocardiographic parameters grouped into 3 types of cardiac mechanics:

- Relaxation parameters such as: E/Ea, Ea
- Contraction parameters such as: Sa, TAPSE
- Overall cardiac pumping ability parameters such as: SVI, CI

The MANOVA p-value from Pallai's Trace will be reported. ((Olson (1976) suggests that Roy's largest root is too likely produce Type I errors and should be avoided, that Wilk's lambda and Hotelling's trace are sensitive to violations of equal covariances in smaller samples, and he recommends Pillai's trace for general use.)

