# AUC0-48h on change in dyspnoea by VAS score

Analysis will be performed only for patients with VAS score at screening different from 100 or missing.

1.0/30/10/2018 Page 20 of 28

AUC0-48h on change in dyspnoea by VAS score will be summarized by treatment group by means of descriptive statistics.

Comparison between treatment groups will be performed by means of an ANCOVA model with AUC0-48h on change in dyspnoea by VAS score as dependent variable, treatment, centre, gender, baseline cTnT (normal  $\leq$ URL, abnormal  $\geq$ URL) and atrial fibrillation (Yes/No) as fixed effects and baseline dyspnoea as covariate.

The number of patients and the number of patients considered in the model will be provided by treatment. P-values of the fixed effects and covariate will also be presented.

The adjusted means for treatments and the 95% CIs will be presented. The differences between the adjusted means for Istaroxime groups versus Placebo will be calculated with the 95% CIs and p-values.

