# **BNP**

BNP and change from baseline will be summarized at each timepoint by treatment group by means of descriptive statistics.

Comparison between treatment groups will be performed by means of an ANCOVA model with change from baseline in BNP at 24 hours as dependent variable, treatment, centre, gender, baseline cTnT (normal <URL, abnormal ≥URL) and atrial fibrillation (Yes/No) as fixed effects and baseline BNP as covariate

The number of patients and the number of patients considered in the model will be provided by treatment. P-values of the fixed effects and covariate will also be presented.

The adjusted means for treatments and the 95% CIs will be presented. The differences between the adjusted means for Istaroxime groups versus Placebo will be calculated with the 95% CIs and p-values.

# Patients with hospital readmissions or emergency visits for cardiovascular reasons within Day 30

The number and percentage of patients with hospital readmissions or emergency visits for cardiovascular reasons within Day 30 will be summarized by treatment groups using descriptive statistics.

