# 9.0 PROGRAMMING SPECIFICATIONS

The following SAS® code will be used to calculate the age of patient:

age = floor((intck('month', date of birth, date of screening)-(day(date of screening)<day(date of birth)))/12)

The following SAS® code will be used to estimate the MMRM:

```
proc mixed data = dataset;
class tmt timepoint centre gender cTnT atr_fib patient;
model change = tmt timepoint tmt*timepoint centre cTnT atr_fib gender baseline
baseline*timepoint / ddfm=kr;
repeated timepoint / subject=patient type=un;
lsmeans tmt tmt*timepoint / cl;
run;
```

where change represents the change from baseline to post-dose values of the variable, tmt the treatment group, timepoint the timepoint, centre the centre, gender the gender (male/female), cTnT the baseline cTnT (normal <URL, abnormal  $\geq$ URL), atr\_fib the atrial fibrillation (Yes/No), baseline the baseline value of the variable and patient the Patient Number.

The variable tmt will be ordered in SAS® in the following order:

- Istaroxime 0.5 μg/kg/min
- Istaroxime 1.0 µg/kg/min
- Placebo

The following SAS® code will be used to estimate the ANCOVA model:

```
proc mixed data = dataset;
class tmt centre gender cTnT atr_fib;
model variable = tmt centre gender cTnT atr_fib predose;
```

1.0/ 30/10/2018 Page 24 of 28

```
lsmeans tmt / cl; run;
```

where variable represents the efficacy variable (AUC on changes in dyspnoea by VAS score or changes in BNP), tmt the treatment group, centre the centre, gender the gender (male/female), cTnT the baseline cTnT (normal <URL, abnormal ≥URL), atr\_fib the atrial fibrillation (Yes/No), predose the pre-dose of efficacy variable.

The variable tmt will be ordered in SAS® in the following order:

- Istaroxime 0.5 μg/kg/min
- Istaroxime 1.0 μg/kg/min
- Placebo

The following SAS code will be used for the Wilcoxon rank sum test for  $T_{max}$ :

```
proc npar1way wilcoxon hl alpha=0.1 data = dataset; class tmt; var Tmax; run;
```

where tmt represents the treatment groups and Tmax the Tmax parameter value for each patient.

The following SAS code will be used for the ANOVA:

```
proc glm data = dataset;
class tmt;
model variable = tmt;
lsmeans tmt / cl;
run;
```

The following SAS code will be used for the MANOVA:

```
proc glm data = dataset;
class tmt;
model variable = tmt;
contrast 'active vs placebo' group 1 -1;
manova h=tmt;
lsmeans tmt / cl;
run;
```

The global test p-value from Pallai's Trace will be reported.

1.0/30/10/2018 Page 25 of 28

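### The primary E/Ea comparison is a valid treatment-only ANOVA of 24 h change at 40 vs 20, but it uses baseline E/Ea only by subtraction and no baseline-adjusted analysis is planned, which usually costs some precision.

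*SAP*

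**What the plan says.** Three parts of the SAP agree on the primary model. Section 7.7.1 compares groups "using an ANOVA with change from baseline in E/Ea at 24 hours as dependent variable, and treatment as covariate". Section 7.2 states that "ANOVA models for echocardiographic parameters will include treatment only". The code in section 9.0 has one right-hand-side term: "model variable = tmt".

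The comparison is made within cohort. Section 7.4 pools placebo across cohorts "with the exception of the echocardiographic parameters that will be analysed separately for each cohort". By section 4.0, each cohort randomises 40 patients to istaroxime and 20 to placebo. The primary test is therefore 40 vs 20 in Cohort 1, and the secondary test is 40 vs 20 in Cohort 2.

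Section 6.5 defines the echocardiographic baseline as the pre-dose Day 1 value. For E/Ea it is used only to form the change score. The other echocardiographic endpoints follow the same pattern: "Comparison between treatment groups will be done using the ANOVA similar to the one used for the primary efficacy endpoint". The MANOVA code also contains treatment only.

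Protocol 14.2 specified a repeated-measures model for E/Ea with baseline and a baseline-by-timepoint term. SAP 1.1 replaces it with the ANOVA and refers to a memo to file, which is not among the documents, for the reasons.

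Every modelled efficacy endpoint that is not echocardiographic keeps its baseline covariate: dyspnoea VAS in its repeated-measures model, the dyspnoea AUC "as fixed effects and baseline dyspnoea as covariate", and BNP "as fixed effects and baseline BNP as covariate".

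**The concern.** Subtracting baseline assumes that each extra unit of baseline E/Ea carries through in full to 24 h. When the true slope is below 1, the change score still contains baseline noise that a fitted slope would remove. The primary comparison has only 20 placebo patients per cohort and no formal sample size calculation behind it (SAP 4.1), so avoidable width in its confidence interval matters. The covariate is already collected (Protocol section 7).

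Two features of the SAP add to the question. The primary endpoint receives less adjustment than the secondary dyspnoea and BNP endpoints. Section 7.7.1 also still says "The adjusted means for treatments and 95% CIs will be presented" and promises p-values for covariates, although the model has nothing to adjust for.

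**Working it through.** **Inputs from the documents.** 40 vs 20 per cohort (SAP 4.0); two-sided alpha 0.05 (SAP 7.4); entry requires E/Ea above 10 (Protocol 4.1). An earlier 6 h study reported E/Ea figures of -3.8 (p = 0.03) at 0.5 µg/kg/min and -1.12 (p = 0.059) at 1.0 µg/kg/min (Protocol 1.2), with 29 patients in both the 0.5 µg/kg/min and placebo groups (SAP 4.1). No power, SD or correlation is stated, so there is no figure of the plan's own to reproduce.

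**Assumed ranges.** r is the correlation between baseline and 24 h E/Ea. k = SD(baseline)/SD(24 h).

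**Step 1: variance ratio, baseline-adjusted to planned ANOVA.** In units of the 24 h variance, the change score has variance 1 + k² - 2rk and the residual after fitting baseline has variance 1 - r². The ratio is (1 - r²)/(1 + k² - 2rk). Estimating one slope with 60 patients multiplies it by about 1 + 1/56 = 1.018.

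| k | r = 0.3 | r = 0.5 | r = 0.7 | r = 0.9 |
|---|---|---|---|---|
| 1 | 0.65 | 0.75 | 0.85 | 0.95 |
| 1, × 1.018 | 0.66 | 0.76 | 0.87 | 0.97 |
| 0.8 | 0.78 | 0.89 | 0.98 | 0.95 |
| 0.7 | 0.85 | 0.95 | 1.00 | 0.83 |

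For k = 1 the standard error falls by 19%, 13%, 8% and 2.5% before the slope penalty. The fitted slope is r/k, so the gain vanishes when r = k (slope 1).

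**Step 2: effect of the entry threshold.** Restricting baseline to values above 10 shrinks its SD and lowers k. As an illustration, take normal baseline and 24 h values with equal SDs before restriction, means of 12, 16 and 20 and SDs of 5 and 8, and cut baseline at 10. Then k runs from 0.70 to 0.97. The ratio is 0.77 to 0.88 if the unrestricted r is 0.5, and 0.86 to 0.93 if it is 0.7. The threshold applies at screening; if the pre-dose Day 1 echo is a separate measurement, the restriction is softer.

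**Step 3: validity of the planned test.** Simulation at 40 vs 20 with r from 0.3 to 0.7 gave type I error of 0.048 to 0.052 for the treatment-only ANOVA, with no bias.

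**Step 4: worst case for adjustment.** At slope 1 with no atrial fibrillation effect, variance rises by 1 + 1/56 = 1.018 with one covariate, or 1 + 2/55 = 1.036 with two. Simulation with baseline and atrial fibrillation (20% prevalence assumed) gave 1.02.

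**Step 5: power, illustration only.** Suppose -3.8 is the difference from placebo, tested by a t-test at 29 vs 29 (56 df). Then t = 2.227, SE = 3.8/2.227 = 1.706, and SD = 1.706/√(2/29) = 6.5. The same step for -1.12 (t = 1.927, SE = 0.581, 29 vs 29 assumed) gives SD 2.2. The SD is therefore not established. For a difference of 3.8 at 40 vs 20, with SE = SD × √(1/40 + 1/20):

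| SD of change | SE | Planned ANOVA | Baseline-adjusted, k = 1, r = 0.5 |
|---|---|---|---|
| 4 | 1.10 | 93% | 97% |
| 5 | 1.37 | 78% | 88% |
| 6.5 | 1.78 | 56% | 67% |
| 8 | 2.19 | 40% | 50% |

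At SD 6.5, the ratios of 0.77 to 0.93 from step 2, with the slope penalty, give about 66% to 58% in place of 67%. At k = r = 0.7 adjusted power is 55%, slightly below the planned model. At SD 2.2 power exceeds 99% either way.

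**The case against.** The strongest case against is that this is a preference about efficiency. The test and interval are valid, the gain may be nil, and a phase II trial with no stated power misses no planned precision. The move to a treatment-only model was deliberate, and its reasons are in a memo that cannot be read here. Changing the primary model again, after the SAP was finalised on 30 October 2018, needs care, and the documents do not show whether the data were still blinded. A pre-specified ANCOVA as sensitivity would close the gap with less disturbance. Including atrial fibrillation but not centre treats two randomisation strata differently. The power figures rest on an uncertain SD.

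Much of this stands as a limit. The memo's reasons are not judged. The power table is illustrative. No precision gain from atrial fibrillation is claimed, because the documents do not say that it predicts change. If unblinding has taken place, the adjusted model belongs as a sensitivity analysis. Centre differs in practice: the number of centres is not given, and fitting each one within a cohort of 60 could use many degrees of freedom.

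The central point is not answered. The primary endpoint has no baseline-adjusted analysis of any kind, the covariate is in hand, and the possible loss from using it is small beside the plausible gain.

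**Conclusion.** The concern holds as a point of precision, and it should be fixed. The planned test is not biased and its error rate is sound, provided that the comparison stays randomised within cohort, that missing 24 h echoes are unrelated to outcome, and that variances are roughly equal.

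With equal SDs and r between 0.3 and 0.9, the plan gives up 5% to 35% of variance before the slope penalty. With baseline restricted as in the illustration, it gives up about 7% to 23%. If the baseline slope is near 1, it gives up nothing. These sizes rest on assumed r and k.

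The loss from not pooling placebo is a separate matter: 40 vs 20 has a standard error 22% larger than 40 vs 40, since √(0.075/0.05) = 1.22. None of that is attributed to the missing covariate.

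**What to change.** Before unblinding, and within each cohort:

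- Make the primary model an ANCOVA of 24 h change in E/Ea on treatment and pre-dose Day 1 E/Ea, with atrial fibrillation included because it is a randomisation stratum. Omit centre, or pool it by country.
- Use the same form at 6 h and for the other echocardiographic endpoints, each with its own baseline.
- For the MANOVA global tests, add the baselines of the parameters in each group, or label the tests as unadjusted.
- Keep the treatment-only ANOVA as a sensitivity analysis.

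The references to adjusted means and covariate p-values in 7.7.1 would then describe the model actually fitted.

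The cost is about two degrees of freedom (residual df from 58 to 56), at most roughly 2% to 4% of variance if neither covariate helps, and short edits to SAP 7.2, 7.7.1, 7.7.2 and the code in 9.0. No new data are needed.
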